## LIST OF ABBREVIATIONS

TERM	DEFINITION	TERM	DEFINITION
AE	Adverse Event	ICH E6	International Conference on Harmonization Guidance for Industry, Good Clinical Practice: Consolidated Guidance
ADE	Adverse Device Effect	ICMJE	International Committee of Medical Journal Editors
ANCOVA	Analysis of Covariance	IDE	Investigational Device Exemption
BMI	Body Mass Index	IFU	Instructions for Use
CFR	Code of Federal Regulations	IPL	Intense Pulse Light
CGAIS	Clinician Global Aesthetic Improvement Scale	ISO	International Organization for Standardization
CIP	Clinical Investigation Plan	IRB	Institutional Review Board
CMP	Clinical Monitoring Plan	MOP	Manual of Procedures
CRF	Case Report Form	NRS	Numeric Rating Scale for pain assessment
CRO	Contract Research Organization	OHRP	Office for Human Research Protections
CV	Curriculum Vitae	PI	Principal Investigator
DCC	Data Coordination Center	PSQ	Patient Satisfaction Questionnaire
DSMB	Data Safety Monitoring Board	QA	Quality Assurance
EC	Ethics Committee	QC	Quality Control
eCRF	Electronic Case Report Form	SAE	Serious Adverse Event
ETE	Expected Treatment Effect	SAP	Statistical Analysis Plan
FDA	Food and Drug Administration	SADE	Serious Adverse Device Effect
FDAAA	Food and Drug Administration Amendments Act of 2007	SGAIS	Subject Global Aesthetic Improvement Scale
GAIS	Global Aesthetic Improvement Scale	SMC	Safety Monitoring Committee
GCP	Good Clinical Practice	SOP	Standard Operating Procedure
GLP	Good Laboratory Practice	UADE	Unanticipated Adverse Device Effect
GMP	Good Manufacturing Practice	USA	United States of America
HIPAA	Health Information Portability and Accountability Act	CGAIS	Clinical Global Aesthetic Improvement Scale
IB	Investigator's Brochure		
ICH	International Committee on Harmonization		

## PROTOCOL SYNOPSIS

Protocol Number:	LMI22001
Protocol Title:	Safety and Efficacy of the Mosaic Ultra Device
Investigational Devices:	Mosaic Ultra
Development Phase:	Pilot
Study Objective:	Evaluate the Safety and Efficacy of the Mosaic Ultra 1550nm system for the treatment of skin tone and texture, facial rejuvenation, photoaging, wrinkles, scars, stretch marks, acne vulgaris and hair loss.
Brief Study Overview:	
Prospective, Multi-Site, Non-Randomized study of up to 210 participants in two treatment groups
 
 
• Group A: Clinical Treatment Arm (n=180)
 
• Group B: Biopsy Arm (n=30)
 
 
Subject's in Group A will be treated with the device with the recommended parameters based on pre-clinical testing and similar device parameters. Subjects will receive up to 5 treatments and then attend follow-ups 30 and 90-days post treatment. Subject's may be asked to participate in an optional biopsy portion of this arm
 
Subject's in group B will be treated at pre-determined parameters based on regulatory body requirements. Subjects will return up to 3 months post treatment. 5 Biopsies will be collected prior to treatment and throughout the follow-up periods.

Number of Sites Enrolling Participants:	3 sites located in the United States
Sample Size:	N = up to 210 treated participants
Participant Population:	Healthy adults, male and female, at least 18 years old who meet the inclusion and exclusion criteria.
Inclusion Criteria:	
 
• Non-smoking, Male or Female
 
• Age 18 – 60 years old
 
• Understands and accepts the obligation not to undergo any other procedures in the areas to be treated.
 
• Participants who are willing and able to comply with all study participation requirements including returning for follow-up visits and abstaining from exclusionary procedures for the duration of the study.
 
• OPTIONAL - Participants who are willing to undergo biopsies.
 

Exclusion Criteria:	
 
• Previous surgical or cosmetic procedure to the target area in the last 6 to 12 months that could interfere with the treatment procedure
 
• A study participant must not be pregnant or have been pregnant in the last 3 months
 
• A recent history of smoking (6 months)
 
• Presence of an active skin disease or condition that may affect wound healing (ie. diabetes myelitis; connective tissue disease; radiation therapy; or chemotherapy)
 
• Seizure disorder caused by bright light
 
• A history of thrombophlebitis
 
• A history of acute infections
 
• A history of heart failure
 

	
 
• Cancer, malignant disease, skin pathology, condition, or allergic reactions that could interfere with evaluation or with the use of typical ancillary medical treatments or care used before, during, or after treatments
 
• Received or is anticipated to receive antiplatelets, anticoagulants, thrombolytics, vitamin E, or anti-inflammatories within 2 weeks prior to treatment
 
• Intolerance or allergy to medications that could be prescribed before or after the procedure (eg, antibiotics, anesthesia)
 
• A history of keloids
 
• A history or evidence of poor wound healing
 
• A history of coagulative disorder or current use of anticoagulant drugs within 2 weeks of study participation
 
• Use of steroids within 2 weeks of study treatments
 
• Patients with implanted pacemaker or defibrillator, or metal pins, or prosthetic joints within 4 cm of treatment area
 
• History of psychoneurosis and/or a history of alcohol or drug abuse
 

Primary Endpoint:	
 
• Group A: Evaluation of randomized before treatment and 3-month follow-up images by blinded evaluators
 
• Group B: Complete wound healing following the treatment assessed by collected biopsies.
 

Secondary Endpoints:	
 
• Adverse Event Assessment
 
• Subject satisfaction
 
• Physician satisfaction
 
• Subject Clinical Global Aesthetic Improvement Scale
 
• Physician Clinical Global Aesthetic Improvement Scale
 
• Histological Evaluation
 

Safety Variables:	
 
• Prior to treatment, the participant's medical history will be reviewed, pregnancy history will be documented, and a physical examination will be conducted.
 
• At each subsequent visit, the participant will be queried about adverse events and changes in concomitant medications, and the treatment area will be visually examined.
 

Study Duration:	The duration from when the study opens to enrollment until completion of data analyses is anticipated to be 18 months.

## 1. KEY ROLES

Persons serving in key roles in the conduct or oversight of this clinical trial are listed in **Table 1.1-1** below.

## 2. INTRODUCTION

### 2.1 BACKGROUND INFORMATION

#### 2.1.1 DEVICE NAME AND INDICATIONS FOR USE

The Mosaic Ultra is an investigational device for dermatological treatments and skin regeneration procedures that require coagulation of soft tissues. The system emits 1550nm laser light at various pulse durations/configurations via optical fiber through a handpiece.

The Mosaic Ultra laser system is a 1550nm Er:Glass laser which delivers energy through an optical fiber system. The device is capable of using three different tips which are the roller tip, static tip (which comes in a circle, rectangle, and square format, as well as a comb tip. Laser energy is delivered when the device is activated via a foot switch. Patient comfort is managed using air cooling.

The clinical trial described in this protocol evaluates clinical outcomes associated with the treatment of various indications. The primary method of evaluation will be the assessment of before and after photography by blinded evaluators. Treated areas and results will be evaluated by both the physician and the subject for both satisfaction and CGAIS.

#### 2.1.2 BRIEF SKIN CONDITION BACKGROUND AND TREATMENT OVERVIEW

The Mosaic Ultra can potentially treat skin tone and texture, facial rejuvenation, photoaging, wrinkles, scars, stretch marks, acne vulgaris and hair loss.

Pigmented lesions refer to a wide range of abnormalities that can be found on the skin, including not limited to lentigos (age spots), solar lentigos (sunspots), and ephelides (freckles). Many people develop brown lesions on their skin from chronic sun exposure, time, and other factors. These can appear on the face, hands, upper chest, and other locations and tend to make the skin look prematurely aged.

Uneven skin tone and skin texture can occur naturally over time as the skin is exposed to UV rays from the sun. This exposure causes the skin to produce melanin which results in the skin having dark spots resulting in the uneven tone.

This same exposure can cause a breakdown of the skin's natural collagen and elastin which typically support healthy skin. As the collagen and elastin breaks down it can cause the skin to dry out and become rougher resulting in an undesired skin texture.

Wrinkling occurs due to a variety of factors but results in the skin folding into itself and instead of appearing smooth the skin has folds, ridges, and creases. Wrinkles can occur as part of the natural ageing process, exposure to the sun, and a large variety of lifestyle and health habits.

Scars are marks on the skin that are left after the body heals from a wound and are typically a sign that the skin did not heal uniformly. Scars can occur due to a variety of wounds such as (but not limited to) acne inflammation, accidental injuries and cut and burns.

Stretch marks, also known as striae, occur when the skin has been rapidly stretched. The most common cause of stretch marks are pregnancy, but they can also occur if a person gains or loses weight in a short period of time. Stretch marks are typically smaller indented streaks and lines on the skin that can come in many colors such as pink, red, black, blue or purple.

Acne vulgaris is a very common skin issue that is a result of hair follicles under the skin becoming plugged or clogged. It results in small red bumps on the skin which can be painful to some patients due to the inflammation of the hair follicles.

Hair loss and hair thinning is a common issue where the hair stops naturally growing in certain spots and is typically only a concern when this occurs on the head. There are a variety of reasons this can occur but the general idea to treat this issue is by promoting cell proliferation, increasing overall cell survival and promoting the anagen phase of the hair follicles.

There are a variety of treatment options such as topical therapies (tretinoin or topical vitamin C), cryotherapy, and various lasers and energy delivery devices that have been developed to improve skin tone and texture, facial rejuvenation, photoaging, wrinkles, scars, stretch marks, acne vulgaris and hair loss.

### 2.1.3 Mechanism of Actions

The Mosaic Ultra is designed for specific clinical indications and emits 1550nm light. The light energy is directed to the treatment zone through an optical fiber coupled with a handpiece.

Laser use in dermatology relies on the basis that certain targets for energy absorption (chromophores) are capable of absorbing energy from specific wavelengths (absorptive band) without exclusively being targeted by their highest absorption peak. The working basis for this concept rests on the principles of selective photothermolysis, in which thermally mediated radiation damage is confined to chosen epidermal and/or dermal structures at the cellular or tissue structural levels. Tissues surrounding these targeted structures, including overlying or immediately neighboring cells, are spared, potentially reducing nonspecific, widespread thermal injury. The three main chromophores (hemoglobin, water, and melanin) in human skin all have broad absorption peaks of light energy, allowing them to be targeted using both broad and specific wavelengths of light.

### 2.1.4 Device Overview

The Mosaic Ultra laser system consists of the following components:

- Main system body
- Laser Delivery System (optical fiber with installed handpiece)
- Foot switch

FIGURE 1: MOSAIC ULTRA LASER SYSTEM COMPONENTS

Figure 3.2 Handpiece configuration

[figure not shown]

TABLE 2: DEVICE SPECIFICATIONS

Items	System Specificaions	
Laser wavelength	1550nm	
Laser medium	Er:Glass	
Laser delivery system	Optical fiber with handpiece installed	
Laser aiming beam	658nm, < 5mW	
Pulse energy	4 ~ 120mJ	
Pulse rate	115.4 ~ 447.4Hz	
Pulse duration	0.235 ~ 6.667ms	
Device Class	CDRH Class	Class IV
	MDR Class	Class IIB
	Applied Part Class	B
	FDA Class	Class II
Radiation Area (mm x mm)	Roller Tip	15x1
	Static Tip	Circle (Diameter)
		2, 4, 6, 8, 10, 12
		Rectangle
		3x10, 5x10, 6x12, 8x12, 8x16, 8x20
		Square
		2x2, 4x4, 6x6, 8x8, 10x10, 12x12, 16x16, 18x18, 20x20
	Comb Tip	12x2
Laser radiation control	Foot switch	
Display system	10.1" Touch LCD Display	

Cooling system	Air cooling
IP rate	Main body: IPX0 Foot switch: IP68
Electrical specifications	AC100~240, 50Hz/60Hz (Fuse AC250V/6.3A) Max Power: 350VA

## 2.2 RATIONALE

In accordance with the definition of “Significant Risk Device” provided in 21 CFR 812.3, the device to be used in this study has been determined to be a Non-Significant Risk device based on the following:

- a) It is not an implant.
- b) It is not purported or represented to be for use in supporting or sustaining human life and do not present a potential for serious risk to the health, safety, or welfare of a participant.
- c) It is not for a use of substantial importance in diagnosing, curing, mitigating, or treating disease or otherwise preventing impairment of human health.
- d) Use of the device does not pose a serious risk to the health, safety, or welfare of a participant.

The current clinical plan is expected to evaluate the safety and effectiveness of the Mosaic Ultra laser system.

## 2.3 POTENTIAL RISKS AND BENEFITS

### 2.3.1 KNOWN POTENTIAL RISKS

This treatment modality was designed to inherently minimize the risk to the participant. As with any laser device treatment, there is a risk of adverse events, skin reactions or side effects. Expected side effects include:

- Discomfort: When a pulse is triggered, it may cause various degrees of discomfort. Some describe the sensation as stinging. A burning sensation may last for up to an hour after treatment.
- Blistering and burns
- Discoloration: Every laser treatment carries the possibility of permanent skin discoloration. Post-inflammatory hyperpigmentation and pigmentation are widely known complications of laser treatment.
- Eye injury: Protective glasses or goggles are provided for operators and assistants. It is extremely important to wear eye protection at all times during treatment to protect the eyes from accidental exposure to laser and serious injury.
- Infection: Every scar left on the skin carries the risk of infection. This risk of infection may also be associated with machines such as the MOSAIC ULTRA laser system. If detected, any infection should properly be treated with topical and/or systemic medications.
- Keloid formation: Scars may become thickened due to excessive growth of fibrous tissue.
- Prolonged redness: A mild case of temporary red spots is an expected reaction. However, if the red spots appear severe or last much longer than expected, do not repeat the treatment until the spots have disappeared. This reaction may vary by patient.

- Scarring: There is a possibility that scars may form due to treatment with the MOSAIC ULTRA laser system. Scars may form locally if treatment procedures are not properly followed, which may lead to exposure to laser, infection or physical irritation of the area such as wiping or rubbing.
- Delayed wound healing/skin textural changes: After laser treatment, the reepithelialization process may not proceed as expected due to the patient's physiological characteristics (e.g. lack of wound healing ability or poor care after treatment). This may result in undesirable changes to the skin texture.
- Temporary bruising

#### 2.3.1.1 MINIMIZATION OF POTENTIAL RISKS

The risks listed above are minimized by treating a small area of the skin and noting the participant's sensation and inflammatory response. Potential risks will be further minimized or reduced by monitoring the participant during the treatment/exposure and observing the skin's response to receiving the treatment/exposure. If the treatment/exposure is not tolerated, the investigator (or delegated clinician) must stop administering the exposure for the participant's safety, and the participant will be followed for adverse events for through resolution of the adverse event and/or 30 days.

#### 2.3.1.2 SAFETY VARIABLES

Prior to the first exposure, the participant's medical history will be reviewed, pregnancy history will be documented, and a physical examination of the treatment area will be conducted to ensure it is free of open wounds. At each subsequent visit, the participant will be queried about adverse events and changes in concomitant medications, and the exposure area will be visually examined.

#### 2.3.2 KNOWN POTENTIAL BENEFITS

There is a potential benefit to participants of this study who are seeking improved appearance of pigmented lesions and vascular lesions of the face. Results of the study may contribute to further the development of the Lutronic Mosaic Ultra laser system.

### 3. OBJECTIVES AND PURPOSE

The objective of this study is evaluate the safety and effectiveness of the Mosaic Ultra laser system for the treatment of cutaneous lesions, periorbital wrinkles, acne scars, and surgical scars.

For subjects in group B, the primary objective will be evaluation of the histological changes via post-treatment biopsies to confirm appropriate wound healing post treatment

### 4. STUDY DESIGN AND AIM

#### 4.1 DESCRIPTION OF THE STUDY DESIGN

This study is a prospective clinical trial to be conducted at three clinical sites. Up to 210 participants will be enrolled and receive study treatment (total enrollment may be more than 210, due to screen failures) if they meet the inclusion/exclusion criteria and provide written informed consent. The study will be used to confirm parameters

and safety across a wide variety of clinical indications. Group A may have up to 180 subjects enrolled into the treatment arm, Group B may have up to 30 patients enrolled into the biopsy arm.

## 4.2 DURATION OF STUDY

The duration from when the study opens to enrollment until completion of data analysis is anticipated to be 18 months.

## 4.3 STUDY ENDPOINTS

### 4.3.1 PRIMARY ENDPOINT

The primary endpoint of this study is:

1. Group A: Selection of post-treatment images when randomized with baseline images as assessed by blinded evaluators
2. Group B: Evaluation of histological samples taken via punch biopsies to observe treatment effect and wound healing.

### 4.3.2 SECONDARY ENDPOINTS

The secondary endpoints of this clinical trial include:

1. Subject satisfaction
2. Physician satisfaction

Table 3: Satisfaction Scale

Score	Rating
6	Extremely Satisfied
5	Satisfied
4	Slightly Satisfied
3	Slightly Dissatisfied
2	Dissatisfied
1	Extremely Dissatisfied

3. Physician CGAIS

4. Subject CGAIS

Table 4: Clinical Global Aesthetic Improvement Scale

Score	Rating	Description
5	Very Much Improved	Optimal cosmetic result in the subject
4	Much Improved	Marked improvement in appearance from the initial condition, but not completely optimal
3	Improved	Obvious improvement in appearance from initial condition, but further treatments may be beneficial
2	No Change	The appearance is essentially the same as the original condition
1	Worsened	The appearance is worse than the original condition

5. Adverse event assessment

#### 4.4 SUCCESS CRITERIA

The study will be considered a success if the following criteria are met:

Group A: Clinical Treatment Arm

1. Blinded evaluators are able to correctly identify the post-treatment image at least 80% of the time
2. The adverse event and side effect profile are acceptable

Group B: Biopsy Arm

1. Wounds induced by the treatment device appropriately healed as assessed by histology.

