#### PRIOR TO TAKING PHOTOGRAPHS:

- Natural Skin; skin washed, and no make-up
- Jewelry removed
- For any body part being treated, ensure a black background is in place
- Treatment area may be marked with a surgical marker prior to photographs

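### The Group A primary endpoint rewards recognising the post-treatment image, not judging it better, so reaching 80% shows a visible difference and not an improvement

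*Combined protocol and SAP*

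**What the plan says.** Section 4.3.1 gives the Group A primary endpoint as "Selection of post-treatment images when randomized with baseline images as assessed by blinded evaluators". The synopsis is less specific: it refers only to blinded evaluation of randomised baseline and 3-month images. Section 4.4 sets two success criteria for Group A. The first is "Blinded evaluators are able to correctly identify the post-treatment image at least 80% of the time". The second is "The adverse event and side effect profile are acceptable", with no definition of acceptable.

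The synopsis states the objective as "Evaluate the Safety and Efficacy of the Mosaic Ultra 1550nm system", and Section 3 as "evaluate the safety and effectiveness of the Mosaic Ultra laser system", each followed by a list of indications.

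Direction of change is recorded on the CGAIS (Section 4.3.2, Table 4), whose lowest grade reads "The appearance is worse than the original condition". The CGAIS is a secondary endpoint rated by the physician and the subject. No blinding is stated for these ratings, and they do not appear in Section 4.4.

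On photographs, Section 6.1 says "Treatment area may be marked with a surgical marker prior to photographs". Its closing checklist asks that follow-up images match baseline in framing, light and position, but does not mention marks.

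**The concern.** Telling before from after is a different task from judging that after is better. Section 2.3.1 lists visible and possibly lasting changes that are not benefits, including scarring and altered skin texture, and warns: "Every laser treatment carries the possibility of permanent skin discoloration". An evaluator who recognises such a change as a laser effect picks the post-treatment image correctly, and the pair adds to the efficacy score. An evaluator who assumes the better image must be the later one scores the same pair as incorrect. The evaluator instruction is not given, so the meaning of the endpoint depends on what each reader happens to assume.

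Criterion 1 is the whole efficacy verdict for Group A. The measures that do record direction cannot change that verdict.

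A smaller, conditional point concerns cues unrelated to treatment effect. Surgical marking is optional and could reveal the order if it differs within a pair. An elective Group A biopsy (Section 6.2, Table 5; Section 6.3.6) could do the same, but only if the site lies in the photographed field. The protocol neither says that it does nor rules it out. The main point stands without these cues.

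**Working it through.** The plan derives no sample size, power or error rate from the 80% threshold, so there is no calculation of its own to reproduce. What follows is illustration.

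**Inputs from the documents.** Threshold 80% (Section 4.4); Group A up to 180 participants (Section 4.1).

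**Assumptions.** One baseline and one post-treatment image per pair with a forced choice, so an indistinguishable pair is guessed correctly 50% of the time. For the exact probabilities in steps 2 and 4, also one read per participant and all 180 evaluable.

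**Step 1: how much recognisable difference gives 80%?** Let x be the share of pairs with any recognisable difference, always identified correctly. Then x + 0.5(1 − x) = 0.80, so x = (0.80 − 0.50)/0.50 = 0.60. Nothing in the criterion requires any of that 60% to be improvement.

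**Step 2: does passing mean anything?** 80% of 180 is 144. Under pure guessing the exact binomial probability of at least 144 correct is about 8 × 10⁻¹⁷, so a pass does demonstrate a detectable difference. With no pair improved and 60% recognisably different, the expected score is 80% and the chance of passing is 0.54. With no pair improved and 70% different, the expected score is 0.70 + 0.5 × 0.30 = 85% and the chance is 0.97.

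**Step 3: identification against better appearance.** Let B be the share visibly better, h the share visibly worse, and r the chance that the evaluator labels the worse image as post-treatment. The remainder is guessed.

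- Identification rate = B + r·h + 0.5(1 − B − h)
- Better-appearance rate = B + 0·h + 0.5(1 − B − h)
- Difference = r·h

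Check with B = 0.40, h = 0.20, r = 1: identification = 0.40 + 0.20 + 0.20 = 0.80; better appearance = 0.40 + 0 + 0.20 = 0.60; difference = 0.20.

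Better-appearance rate when the identification rate is 80%:

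| h | r = 0 | r = 0.5 | r = 1 |
|---|---|---|---|
| 5% | 80% | 77.5% | 75% |
| 10% | 80% | 75% | 70% |
| 20% | 80% | 70% | 60% |

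**Step 4: effect on the pass rule.** Take 30% improved, 30% worse and always recognised, and 40% indistinguishable. Identification is 0.30 + 0.30 + 0.20 = 80%, and the chance of reaching 144 of 180 is 0.54. Scored on better appearance the rate is 0.30 + 0 + 0.20 = 50%, and the chance is below 0.0001.

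**The case against.** The strongest reply is that evaluators of aesthetic photographs will naturally take the better image to be the later one. Worsened pairs would then count as errors and there would be no inflation; this is the r = 0 column. That may be how the read works in practice, but the plan does not say so, and a primary endpoint should not rest on an unwritten assumption.

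Second, the study succeeds only if both Group A criteria are met, and the harms in question are what criterion 2 reviews. The treated area is examined at each subsequent visit (Section 2.3.1.2), and all expected effects and adverse events are collected (Section 7.1.1). Widespread worsening might well fail the study on criterion 2. That stands in part, although the criterion has no stated limit. It does not meet the main point, because absence of unacceptable harm is not evidence of benefit.

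Third, this is a non-randomised pilot with descriptive summaries, and readers will see CGAIS and satisfaction results beside the identification rate. That is true and useful. Section 4.4 nevertheless declares success or failure, and those ratings are outside it.

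Fourth, the worsening and recognition rates are invented. They are, and the larger values of h are severe for images taken 90 days after the last treatment. The figures show what the criterion allows, not what is likely. They also do not quantify the marking and biopsy cues, which remain minor.

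**Conclusion.** The concern holds. It rests on the text: Sections 4.3.1 and 4.4 score only recognition of the post-treatment image, and no part of the plan adds a direction to the blinded read. A pass on criterion 1 would establish a detectable difference but would not by itself establish the efficacy or effectiveness named as the objective.

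The size cannot be determined from the documents. The overstatement relative to a better-appearance score equals r·h, from zero if evaluators never label a worsened image as post-treatment up to the full share of worsened pairs if they always do. These figures depend on the assumed 50% guess rate and on assumed values of r and h. The conclusion about what the endpoint measures does not. The change should be made before the blinded read, because a recorded before/after pick cannot be turned into a judgement of improvement without a second read.

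**What to change.** In Sections 4.3.1 and 4.4, keep the blinded evaluators and randomised pairs but change the question. For each pair the evaluator chooses the image with the better appearance for the treated indication, and the pair is a success only if that image is the post-treatment one. Give evaluators short guidance on what better means for each indication, and align the synopsis.

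In Section 6.1, require the baseline and follow-up photographs used for the blinded read to be unmarked or identically marked. Where a biopsy site is visible in the field, crop or mask it in both images of the pair.

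The cost is one line each in 4.3.1, 4.4 and the 6.1 checklist, the matching synopsis wording, brief reader guidance, and minor image preparation where a biopsy site shows. No extra participants, visits, photographs or evaluators are needed. The drawback is that the observed rate may be lower than a pure identification rate, so the 80% threshold may be harder to reach.
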